8.1.3 Full Analysis Set

The **Study 106 Full Analysis Set (106-FAS)** is defined the same as the FAS definition in the SAP of Study 106 Part B.

The **Open-label Extension Full Analysis Set (OLE-FAS)** for Part A is defined as all enrolled subjects who have received at least 1 dose of study drug in the corresponding Part.

The **Cumulative TC Set** includes subjects who were enrolled and received at least one dose of study drug during the parent study (445-106 Part B) and/or received at least one dose of study drug during the OLE Study.

8.2 Analysis Sets for Final Analysis

8.2.1 All Subjects Set

The **Open-label Extension All Subjects Set** is defined as all subjects who were enrolled (defined as subject having data in the clinical database) in the open-label extension (OLE) study (Study 445-107). This analysis set will be used for individual subject data listings and disposition summary tables in the Week 144 IA and the final analysis unless otherwise specified.

8.2.2 Safety Set

The **Open-label Extension Safety Set (OLE-SS)** is defined as all subjects who have received at least 1 dose of study drug in the OLE study. This analysis set will be used for all safety analyses in the Week 144 IA and the final analysis unless otherwise specified.

8.2.3 Full Analysis Set

The **Study 106 Full Analysis Set (106-FAS)** is defined the same as the FAS definition in the SAP of Study 106 Part B.

The **Open-label Extension Full Analysis Set (OLE-FAS)** is defined as all enrolled subjects who have received at least 1 dose of study drug in the OLE study.

The **(OLE) Cumulative TC Set** includes subjects who were enrolled and received at least one dose of study drug during the parent study (445-106 Part B) and/or received at least one dose of study drug during the OLE Study.

9 ANALYSIS PERIOD

The analysis period used for safety and efficacy endpoints in the final analysis is described below.

9.1 Parent Study Efficacy Period

The definition of this analysis period is the same as the PEx analysis period defined in the SAP for Study 445-106 Part B. This analysis period will be used with the parent study efficacy analysis set (106-FAS) to analyze the efficacy data during the parent study.

9.2 Analysis Period for Part A Analysis

OLE Efficacy Period for Part A: Time from the first dose of study drug in the corresponding Part until the last efficacy assessment, which may be collected up to the corresponding Week 96 Visit or the earlier of Day 673 and the end of study participation if subject does not have the corresponding Week 96 Visit in the same Part. This analysis period will be used with the OLE-FAS for the corresponding Part to analyze efficacy data during the corresponding Part.

OLE Safety Period for Part A: Time from the first dose of study drug in the corresponding Part to 28 days after the last dose of the study drug in the corresponding Part or to the completion date of study participation (as defined in Section 9.1.5 of the CSP), whichever occurs first.

The completion date of study participation will be obtained from the end of study page of the eCRF.

The **Treatment-emergent (TE) Period for Part A** is same as the OLE Safety Period for the corresponding Part.

Cumulative TC Efficacy Period for Part A: For subjects who enrolled in Part A, the time from the first dose of study drug in the parent study (445-106 Part B) until the last efficacy assessment in Part A, which may be collected up to the Part A Week 96 Visit or the earlier of Day 673 in Part A and the end of study participation if subject does not have the Part A Week 96 Visit. For subjects who did not enroll in the OLE study and were enrolled and received study drug in the parent study, definition of this analysis period is the same as the parent study efficacy period.

9.3 Analysis Period for Final Analysis

OLE Efficacy Period: Time from the first dose of study drug in the OLE study to the last efficacy assessment, which may be collected up to OLE Part B Week 96 Visit or the earlier of Day 1345 and the end of study participation if subject does not have the OLE Part B Week 96. This analysis period will be used with the OLE-FAS to analyze efficacy data in the Week 144 IA and the final analysis.

OLE Safety Period: Time from the first dose of study drug in the OLE study to 28 days after the last dose of the study drug in the OLE study or to the completion date of study participation (as defined in Section 9.1.5 of the CSP), whichever occurs first.

The completion date of study participation will be obtained from the end of study page of the eCRF.

The **OLE Treatment-emergent (TE) Period** is same as the OLE Safety Period.

The OLE Cumulative TC Efficacy Period: For subjects who enrolled in the OLE study, the time from the first dose of study drug in the parent study (445-106 Part B) until the last efficacy assessment in the OLE study, which may be collected up to the Part B Week 96 Visit or the earlier of Day 1345 and the end of study participation if subject does not have the Part B Week 96 Visit. For subjects who did not enroll in the OLE study and were enrolled and received study drug in the parent study, definition of this analysis period is the same as the parent study efficacy period.

The Cumulative TC Efficacy periods will be used with the Cumulative TC sets for analysis of PEx data.

10 STATISTICAL ANALYSIS

10.1 General Considerations

The Schedule of Assessments is provided in Section 3 of the CSP. The precision standards for reporting safety and efficacy variables are provided in an internal Biometrics document that specifies the programming rules including the precision for derived variables.

Continuous variables will be summarized using the following descriptive summary statistics: the number of subjects (n), mean, standard deviation (SD), median, minimum value (min), and maximum value (max).

Categorical variables will be summarized using counts and percentages. Percentages will be presented to 1 decimal place.

Baseline unless otherwise specified, is defined as the most recent non-missing measurement (scheduled or unscheduled) collected prior to the first dose of study drug in the parent study.

Note: for subjects who take Orkambi or Symdeko (branded as Symkevi in Europe) during the 28 days before the screening visit, the data collected at screening visit will not be used for baseline derivation for spirometry, sweat chloride and LCI.

Absolute change from baseline will be calculated as Post-baseline value – Baseline value.

Relative change from baseline will be calculated and expressed in percentage as $100\% \times (\text{Post-baseline value} - \text{Baseline value}) / \text{Baseline value}$.

Unscheduled visits: Unscheduled visit measurements will be included in analysis as follows:

- In scheduled visit windows per specified visit windowing rules
- In the derivation of baseline and last on-treatment measurements
- In the derivation of maximum and minimum values during TE period, and maximum and minimum change from baseline values during TE period for safety analyses
- In individual subject data listings as appropriate

Visit windowing rules: The analysis visit windows for protocol-defined visits are provided in Appendix A.

Incomplete/missing data will not be imputed, unless specified otherwise.

Outliers: No formal statistical analyses will be performed to detect or remedy the presence of statistical outliers, unless specified otherwise.

Multiplicity: There will be no multiplicity adjustment as no hypothesis test is planned for safety analysis, unless specified otherwise.

10.2 Background Characteristics

10.2.1 Background Characteristics for Part A

10.2.1.1 Subject Disposition

The number of subjects in the following categories will be summarized based on the Open-label Extension All Subjects Set for Part A:

- Open-label Extension All Subjects Set
- Open-label Extension Safety Set
- Open-label Extension Full Analysis Set
- Never dosed

The number and percentage (based on the OLE-FAS for Part A) of subjects in each of the following disposition categories will be summarized:

- Completed treatment
- Prematurely discontinued treatment and the reason for discontinuation
- Completed study
- Prematurely discontinued the study and the reason for discontinuation
- Rolled over to Part B (for Part A only).

Additional disposition categories may be provided for interim analysis, e.g. completed Week 24 Visit and prematurely discontinued treatment before Week 24 Visit and the reason for discontinuation.

A listing will be provided for subjects who discontinued treatment or who discontinued study with reasons for discontinuation.

10.2.1.2 Demographics and Baseline Characteristics

Demographics and baseline characteristics will be summarized based on the OLE-FAS for Part A.

Demographic data will include the following:

- Age at baseline (in years)
- Sex (male, female)
- Ethnicity (Hispanic or Latino, not Hispanic or Latino, and not collected per local regulations)
- Race (White, Black or African American, Asian, American Indian or Alaska Native, Native Hawaiian or Other Pacific Islander, Other, and not collected per local regulations)
- Geographic region (North America, Europe [including Australia])

Baseline characteristics will include the following:

- Weight group (<30 kg, and \geq 30 kg)
- Weight (kg)

- Weight z-score
- Height (cm)
- Height z-score
- BMI (kg/m²)
- BMI z-score

Disease characteristics will include the following:

- CFTR genotype group (F/F, F/MF)
- ppFEV₁ at baseline (<70, ≥70 to ≤90, and >90)
- ppFEV₁ at baseline (continuous)
- Sweat chloride at baseline (continuous)
- CFQ-R respiratory domain score at baseline (child's version; continuous)
- LCI_{2.5} at baseline (continuous)
- Prior use of CFTR modulator (Yes, No)
- Prior use of dornase alfa (Yes, No)
- Prior use of azithromycin (Yes, No)
- Prior use of inhaled antibiotic (Yes, No)
- Prior use of any bronchodilator (Yes, No)
- Prior use of any inhaled bronchodilator (Yes, No)
- Prior use of any inhaled hypertonic saline (Yes, No)
- Infection with *Pseudomonas aeruginosa* within 2 years prior to screening of the parent study (Positive, Negative)

Prior medication use definition is same as that for the baseline characteristics summary presented in the parent study.

In addition, the following data listings will also be provided:

- Informed consent/assent;
- Inclusion/Exclusion criteria violation for subjects with any such violations.

10.2.1.3 Medical History

Medical history will be coded using the Medical Dictionary for Regulatory Activities (MedDRA). For the OLE-FAS for Part A, medical history will be summarized descriptively by system organ class (SOC) and preferred term (PT). The corresponding data listing will also be provided.

10.2.1.4 Prior and Concomitant Medications

Medications will be coded using the World Health Organization Drug Dictionary (WHODrug) and categorized as follows:

- **Prior medication:** any medication that administered during the 56 days before the first dose of study drug in Part A.
- **Concomitant medication:** medication continued or newly received during the OLE Safety Period for Part A.
- **Post-treatment medication:** medication continued or newly received after the OLE Safety Period for Part A.

A given medication may be classified as follows: prior, concomitant, post-treatment, both prior and concomitant, both concomitant and post-treatment, or prior, concomitant, and post-treatment.

If a medication has a completely missing or partially missing start date or stop date and it cannot be determined whether it was taken before the first dose date of Part A, concomitantly during the OLE Safety Period for Part A, or after the OLE Safety Period for Part A, it will be classified as prior, concomitant, and post-treatment. Details for imputing missing or partial start and/or stop dates of medication are described in [Appendix B](#).

Concomitant medications will be summarized descriptively for the OLE-FAS for Part A using frequency tables by 1) preferred name (PN); and 2) anatomic class (ATC) level 1, ATC level 2, and PN. Prior medications will also be summarized the same way as concomitant medications. All medications will be listed for each subject.

10.2.1.5 Study Drug Exposure

Study drug exposure summaries will be based on the OLE-SS for Part A.

Duration of study drug exposure (in days) will be calculated as [last dose date – first dose date + 1 day] within the OLE Safety Period for Part A, regardless of study drug interruption. For subjects who are still on study drug at IA data cutoff date, the corresponding date will be used as the last dose date for the exposure calculation.

Study drug exposure (in weeks) will be summarized descriptively by the number of subjects (n), mean, SD, median, min, and max. It will also be summarized into the following categories: <=24 weeks, >24 to <=48 weeks, >48 to <=72 weeks, >72 to <=96 weeks, >96 weeks. Additionally, the total study drug exposure, defined as the sum total of the study drug exposure across all subjects (in patient-weeks and patient-years), will be provided.

10.2.1.6 Study Drug Compliance

Study drug compliance will be summarized based on the OLE-FAS for Part A.

Study drug compliance will be calculated as: $100 \times [1 - (\text{total number of days of study drug interruption started before last dose of study drug}) / (\text{duration of study drug exposure in days})]$. A study drug interruption on a given day is defined as an interruption of any study drug dose or component on that day.

Study drug compliance will be summarized descriptively by the number of subjects (n), mean, SD, median, min, and max. It will also be summarized in categories: <80% and $\geq 80\%$ using frequency tables.

In addition, percentage of tablets taken will be calculated using the following formula: $100 \times [(total\ number\ of\ tablets\ dispensed) - (total\ number\ of\ tablets\ returned)] / (total\ number\ of\ tablets\ planned\ to\ be\ taken\ per\ day \times duration\ of\ study\ drug\ exposure\ in\ days)$. A summary similar to that for study drug compliance will be produced based on the OLE-FAS for Part A.

10.2.1.7 Important Protocol Deviations

An important protocol deviation (IPD) is a deviation that may significantly affect the completeness, accuracy, or reliability of the study data or that may significantly affect a subject's rights, safety, or well-being. A protocol deviation review team will categorize IPDs according to the protocol deviation plan during the study.

Protocol deviations that should be considered as potential IPDs include, but are not limited to:

- Subject was enrolled in the study despite not satisfying one or more inclusion/exclusion criterion
- Subject was less than 80% compliant with study drug for non-safety reasons
- Subject received prohibited concomitant medications
- Subject received the wrong treatment or incorrect doses

IPDs will be summarized descriptively based on the OLE-FAS for Part A. Additionally, IPDs will be provided in an individual subject data listing.

10.2.2 Background Characteristics for the OLE study

10.2.2.1 Subject Disposition

The number of subjects in the following categories will be summarized based on the Open-label Extension All Subjects Set:

- Open-label Extension All Subjects Set
- Open-label Extension Safety Set
- Open-label Extension Full Analysis Set
- Never dosed

The number and percentage (based on the OLE-FAS) of subjects in each of the following disposition categories will be summarized:

- Completed treatment in Part A
- Prematurely discontinued treatment in Part A and the reason for discontinuation
- Completed study in Part A
- Prematurely discontinued the study in Part A and the reason for discontinuation
- Rolled over to Part B

- Completed treatment in Part B
- Prematurely discontinued treatment in Part B and the reason for discontinuation
- Completed study in Part B
- Prematurely discontinued the study in Part B and the reason for discontinuation

Additional disposition categories may be provided for interim analysis (e.g., ongoing at Part B Week 48 Visit, prematurely discontinued treatment before Part B Week 48 Visit and the reason for discontinuation).

A listing will be provided for subjects who discontinued treatment or who discontinued study with reasons for discontinuation.

10.2.2.2 Demographics and Baseline Characteristics

Demographics and baseline characteristics will be summarized based on the OLE-FAS. Demographic data will include the following:

- Age at parent study baseline (in years)
- Sex (male, female)
- Ethnicity (Hispanic or Latino, not Hispanic or Latino, and not collected per local regulations)
- Race (White, Black or African American, Asian, American Indian or Alaska Native, Native Hawaiian or Other Pacific Islander, Other, and not collected per local regulations)
- Geographic region (North America, Europe [including Australia])

Baseline characteristics based on parent study will include the following:

- Weight group (<30 kg, and \geq 30 kg)
- Weight (kg)
- Weight z-score
- Height (cm)
- Height z-score
- BMI (kg/m^2)
- BMI z-score

Disease characteristics based on parent study will include the following:

- CFTR genotype group (F/F, F/MF)
- ppFEV₁ at baseline (<70, \geq 70 to \leq 90, and $>$ 90)
- ppFEV₁ at baseline (continuous)
- Sweat chloride at baseline (continuous)
- CFQ-R respiratory domain score at baseline (child's version; continuous)

- LCI_{2.5} at baseline (continuous)
- Prior use of CFTR modulator (Yes, No)
- Prior use of dornase alfa (Yes, No)
- Prior use of azithromycin (Yes, No)
- Prior use of inhaled antibiotic (Yes, No)
- Prior use of any bronchodilator (Yes, No)
- Prior use of any inhaled bronchodilator (Yes, No)
- Prior use of any inhaled hypertonic saline (Yes, No)
- Infection with *Pseudomonas aeruginosa* within 2 years prior to screening of the parent study (Positive, Negative)

Prior medication use definition is same as that for the baseline characteristics summary presented in the parent study.

In addition, the following data listings will also be provided:

- Informed consent/assent;
- Inclusion/Exclusion criteria violation for subjects with any such violations.

10.2.2.3 Medical History

Medical history will be coded using the MedDRA. For the OLE-FAS, medical history will be summarized descriptively by SOC and PT. The corresponding data listing will also be provided.

10.2.2.4 Prior and Concomitant Medications

Medications will be coded using the World Health Organization Drug Dictionary (WHODrug) and categorized as follows:

- **Prior medication:** any medication that administered during the 56 days before the first dose of study drug in the OLE study.
- **Concomitant medication:** medication continued or newly received during the OLE Safety Period.
- **Post-treatment medication:** medication continued or newly received after the OLE Safety Period.

A given medication may be classified as follows: prior, concomitant, post-treatment, both prior and concomitant, both concomitant and post-treatment, or prior, concomitant, and post-treatment.

If a medication has a completely missing or partially missing start date or stop date and it cannot be determined whether it was taken before the first dose date in the OLE study, concomitantly during the OLE Safety Period, or after the OLE Safety Period, it will be classified as prior, concomitant, and post-treatment. Details for imputing missing or partial start and/or stop dates of medication are described in [Appendix B](#).

Concomitant medications will be summarized descriptively for the OLE-FAS using frequency tables by 1) preferred name (PN); and 2) anatomic class (ATC) level 1, ATC level 2, and PN. Prior medications will also be summarized the same way as concomitant medications. All medications will be listed for each subject.

10.2.2.5 Study Drug Exposure

Study drug exposure summaries will be based on the OLE-SS.

Duration of study drug exposure (in days) will be calculated as [last dose date – first dose date + 1 day] within the OLE Safety Period, regardless of study drug interruption. For subjects who are still on study drug at IA data cutoff date, the corresponding cutoff date will be used as the last dose date for the exposure calculation.

Study drug exposure (in weeks) will be summarized descriptively by the number of subjects (n), mean, SD, median, min, and max. It will also be summarized into the following categories: <=24 weeks, >24 to <=48 weeks, >48 to <=72 weeks, >72 to <=96 weeks, >96 to <=120 weeks, >120 to <=144 weeks, >144 to <=168 weeks, >168 to <=192 weeks, >192 weeks. Additionally, the total study drug exposure, defined as the sum total of the study drug exposure across all subjects (in patient-weeks and patient-years), will be provided.

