^d Subjects whose Part B Day 1 Visit is on the same day or within 1 calendar day as the Part A Week 96 Visit do NOT have to repeat any Part B Day 1 assessments that were specified to be performed at the Part A Week 96 Visit. Subjects whose Part B Day 1 Visit is more than 1 calendar day after the Part A Week 96 Visit must complete all assessments specified for the Part A Week 96 AND Part B Day 1 Visits.

Table 3-2 Study VX19-445-107: Part B Treatment Period and Safety Follow-up Visit

Event/Assessment ^a	Part B Treatment Period (96 weeks)					Part B ETT Visit ^b	Part B Safety Follow-up Visit ^c (28 ± 7 Days After Last Dose of Study Drug)	Comments
	Day 1 ^d	Weeks 4, 8, 16, 20, 28, 32, 40, 44, 52, 56, 64, 68, 76, 80, 88, 92 (± 5 Days)	Weeks 12, 36, 60, 84 (± 5 Days)	Weeks 24, 48, 72 (± 5 Days)	Week 96 (± 5 Days)			
Pulse oximetry	X		X	X	X	X	X	Performed after subject has been at rest for at least 5 minutes (Section 11.5.3).
Standard 12-lead ECG	X			X	X	X	X	Performed after subject has been at rest for at least 5 minutes (Section 11.5.4).
Spirometry	X		X	X	X	X	X	Should be performed pre-bronchodilator at approximately the same time at each visit (Section 11.3.1).
Sweat chloride	X			X	X	X		At each time point, 2 samples will be collected (1 sample from each arm; Section 11.3.2).
Pregnancy test (all female subjects)	urine	urine	urine	urine	serum	serum	serum	At telephone contact visits, a urine pregnancy test will be performed with a home kit provided by the study site (Section 11.5.2).
Serum chemistry	X		X	X	X	X	X	Section 11.5.2
Hematology	X		X	X	X	X	X	Section 11.5.2
Coagulation	X			X	X	X	X	Section 11.5.2
Urinalysis	X			Week 48	X	X		Section 11.5.2
Multiple breath washout	X			X	X	X		Performed in multiple replicates, pre-bronchodilator, and before the spirometry assessment (Section 11.3.3).
Blood biomarker sample	X			Week 48	X	X		Section 11.4.2
FE-1	X			Week 48	X	X		Samples may be collected by the subject's caregiver up to 24 hours before the study visit (e.g., at home). The sample may be collected pre- or postdose (Section 11.4.1).
IRT	X			X	X	X		Section 11.4.1

Table 3-2 Study VX19-445-107: Part B Treatment Period and Safety Follow-up Visit

Event/Assessment ^a	Part B Treatment Period (96 weeks)					Part B ETT Visit ^b	Part B Safety Follow-up Visit ^c (28 ± 7 Days After Last Dose of Study Drug)	Comments

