12.3 Statistical Analysis

12.3.1 General Considerations

Continuous variables will be summarized using the following descriptive summary statistics: the number of subjects (n), mean, SD, median, minimum value (min), and maximum value (max). The precision of the measurement for each continuous variable will be specified in the SAP. Unless otherwise specified, min and max values will be reported with the same precision as the units of the raw data. The mean, median, and SD will be reported to 1 additional decimal

place. Any values that require a transformation to standard units (metric or SI) will be converted with the appropriate precision.

Categorical variables will be summarized using counts and percentages. Percentages will be presented to 1 decimal place.

The baseline value, unless otherwise specified, will be the most recent non-missing measurement (scheduled or unscheduled) collected before the first dose of study drug in the parent study. For assessments collected in replicates, the baseline will be defined as the average of non-missing values.

Change (absolute change) from baseline will be calculated as post-baseline value – baseline value.

The **Efficacy Analysis Period** for each Part will include the time from the first dose of study drug to the last scheduled efficacy visit in the corresponding Part, unless otherwise specified.

The **Treatment-emergent (TE) Period** for each Part will include the time from the first dose of study drug to 28 days after the last dose of the study drug or to the date of completion of study participation in the corresponding Part (as defined in Section 9.1.5), whichever occurs first.

Part A and Part B data will be analyzed separately, using the respective analysis set, efficacy analysis period, and TE period for each Part. For analysis of the number of PEx, events in the parent study and this study (Parts A and B, as applicable) may also be combined.

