12.3.2.4 Study Drug Exposure and Compliance

Study drug exposure will be summarized separately for each Part based on the OL-SS, defined as the last day of study drug in each Part minus the first day of study drug in each Part plus 1, regardless of study drug interruption.

Study drug compliance will be summarized based on the OL-FAS, and will be calculated as: $100 \times [1 - (\text{total number of days of study drug interruption in each Part}) / (\text{duration of study drug exposure in days in each Part})]$. A study drug interruption on a given day is defined as an interruption of any study drug on that day.

In addition, percentage of tablets taken will also be summarized based on the OL-FAS, and will be calculated as: $100 \times [(\text{total number of tablets dispensed in each part}) - (\text{total number of tablets returned in each Part})] / (\text{total number of tablets planned to be taken per day} \times \text{duration of study drug exposure in days for each Part})$.

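### The SAP's pooled OLE exposure counts days off study drug between Part A and Part B, which the protocol's per-Part rule leaves out

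*SAP*

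**What the plan says.** **Pooled rule (SAP).** Section 9.3 sets one OLE Safety Period for the Week 144 interim and final analyses. It starts at the first OLE dose and runs "to 28 days after the last dose of the study drug in the OLE study or to the completion date of study participation", whichever is earlier. The OLE treatment-emergent (TE) Period "is same as the OLE Safety Period". Section 10.2.2.5 takes exposure as last minus first dose date plus 1 "within the OLE Safety Period, regardless of study drug interruption". Section 10.2.2.6 uses that duration as the denominator of interruption-based compliance, and multiplies it by planned daily tablets for the percentage of tablets taken. No rule removes time between Parts.

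**Per-Part rule (protocol).** Section 12.3.2.4 has exposure "defined as the last day of study drug in each Part minus the first day of study drug in each Part plus 1". Section 12.3.1 sets the TE Period for each Part, "from the first dose of study drug to 28 days after the last dose of the study drug" or to completion of participation in that Part, if earlier.

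**Transition between Parts (protocol).** Section 9.1.1 makes the Part A Week 96 Visit the start of Part B treatment. The same section and Table 3-2, footnote d, also cover a later start: "Subjects whose Part B Day 1 Visit is more than 1 calendar day after the Part A Week 96 Visit must complete all assessments" for both visits. No upper limit is given. The 28-day condition in 9.1.2 only waives the Safety Follow-up Visit; it does not cap the gap.

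**Declared change.** SAP 3.1 states that safety data from the two Parts are pooled. It does not mention how time between Parts is handled.

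**The concern.** Part A dosing ends the evening before the Part A Week 96 Visit, and Part B dosing starts at Part B Day 1. If those visits are apart, the subject takes no study drug under either Part in between. The pooled SAP rule nevertheless counts those days as exposure and as TE time, although they lie outside both treatment periods.

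Four outputs are touched: total patient-years and the exposure classes, both compliance measures, the set of events called treatment-emergent, and possibly the exposure-adjusted event rates. Long-term safety is the primary objective, so the exposure base should mean what the reader takes it to mean.

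**Working it through.** **Inputs**
- Planned dosing is 96 weeks = 672 days per Part (Protocol Tables 3-1 and 3-2). Visit windows of ±5 days are ignored.
- g = days off study drug between the last Part A dose and the first Part B dose. This is an assumption, shown for 1 to 84 days.
- 64 subjects enrolled (SAP 7.2). The number entering Part B is not given; 70% to 100% is assumed, all completing.

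**1. The plan's own timeline.** SAP Table 13-2 counts days from the first OLE dose. Part B Week 12: (96 + 12) × 7 + 1 = 757. Week 48: (96 + 48) × 7 + 1 = 1009. Week 96: (96 + 96) × 7 + 1 = 1345. The protocol's total duration is 96 + 96 + 4 = 196 weeks. All four match the documents, and all imply g = 0.

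**2. Exposure and tablets for a full completer.** Per-Part sum: 672 + 672 = 1344 days. SAP 10.2.2.5: 672 + g + 672 = 1344 + g. For a perfect adherer the daily tablet count cancels, so the percentage of tablets taken is 100 × 1344/(1344 + g).

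| g (days) | SAP exposure (days) | Excess, g/1344 | Tablets taken |
|---|---|---|---|
| 0 | 1344 | 0 | 100% |
| 1 | 1345 | 0.07% | 99.93% |
| 7 | 1351 | 0.52% | 99.48% |
| 28 | 1372 | 2.08% | 97.96% |
| 84 | 1428 | 6.25% | 94.12% |

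At Part B Week 48 the base is 672 + 336 = 1008 days, and the excess is 0.69%, 2.78% and 8.33% for 7, 28 and 84 days.

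**3. Exposure class.** 1344/7 = 192.0 weeks, the top edge of the >168 to ≤192 class. One gap day gives 1345/7 = 192.14 weeks, so any gap moves this completer to the >192 class.

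**4. Interruption-based compliance.** Let d be the true interruption days within Parts. The per-Part basis gives 1 − d/1344. If the gap is not recorded as an interruption, the SAP gives 1 − d/(1344 + g), which is too high whenever d > 0. If it is recorded, the SAP gives 1 − (d + g)/(1344 + g), which is lower. For example, with d = 28 and g = 28: 97.92% per Part, 97.96% if not recorded, 95.92% if recorded. The SAP does not say which applies.

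**5. Total exposure.** If 90% of the 64 enter and complete Part B, dosing time is (64 + 57.6) × 672 / 365.25 = 223.7 patient-years.
- 10% of entrants with 28 days: 57.6 × 0.10 × 28 / 365.25 = 0.44 patient-years, +0.20% (0.17% to 0.21% over 70% to 100% entry).
- 25% with 84 days: 3.31 patient-years, +1.48% (1.29% to 1.56%).
- All with 28 days: 4.42 patient-years, +1.97% (1.72% to 2.08%).

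**6. TE Period.** The Part A TE Period already has a tail of up to 28 days. The time added by pooling is therefore mainly the part of a gap beyond 28 days, and more if Part A participation was completed earlier. Any AE recorded more than 28 days after the last Part A dose but before Part B would count as treatment-emergent only under the pooled rule.

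**7. Exposure-adjusted rates.** SAP 10.4.2.1 plans them without defining the denominator. If it is the exposure of 10.2.2.5, a rate E/T becomes (E + e)/(T + g), where e is the number of added gap events. It falls if e/g < E/T and rises if e/g > E/T. With e = 0, a full completer's rate is multiplied by 1344/1372 = 0.980 at 28 days and 1344/1428 = 0.941 at 84 days. AE collection may also lapse in a gap, because protocol 13.1.1.3 ends it at completion of participation and Table 3-2 places Part B consent at Part B Day 1. The documents do not fix e, so the direction is open.

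**The case against.** The strongest reply is that no gap is planned. Protocol 9.1.1 starts Part B at the Part A Week 96 Visit, and the 196-week duration and the SAP target days assume the same. That stands: a late Part B Day 1 is foreseen but is not the default.

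Second, ignoring interruptions is a declared convention, also used in protocol 12.3.2.4 and in SAP 10.2.1.5 for Part A. This stands for interruptions within a Part. In both places, however, the convention works inside one Part; extending it over time outside both treatment periods is new.

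Third, SAP 3.1 discloses the pooling, Part A keeps its own exposure and TE definitions, and safety is descriptive without testing. All true, and it limits the consequence. But pooling data does not require counting the time between Parts, and 3.1 does not say that it will be counted.

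Fourth, the OLE Safety Period also ends at completion of participation, if earlier, and a gap over 28 days would not waive the Part A Safety Follow-up Visit. But ending a Part B entrant's period at a Part A completion date would drop all of that subject's Part B data. That cannot be meant in a pooled analysis with exposure classes up to >192 weeks.

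**Conclusion.** The point holds as a minor correction. For any subject with a gap, the SAP's pooled rule counts days off study drug as exposure, contrary to the protocol's per-Part definition. The excess is exactly g days per subject. The percentages above assume full dosing in both Parts. Gap lengths and the number of subjects affected are not in the documents, and the effect is zero if every transition was same-day.

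Three stronger readings are tempting but not supported:
- A reader might infer that exposure-adjusted rates are biased downward. The denominator is undefined, and gap events as well as gap time may enter, so the net direction is unknown.
- A reader might infer that these rates are the main scale for pooled safety. SAP 10.4.2.1 presents counts and percentages alongside them, and protocol 12.3.4.1 makes them optional.
- A reader might infer that long gaps are expected, or that all gap events are reclassified. The gap lengths here are illustrations only, and the per-Part rule already allows a tail of up to 28 days.

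**What to change.** - **SAP 10.2.2.5:** define OLE exposure as Part A duration plus Part B duration, each last minus first dose date plus 1 within that Part.
- **SAP 10.2.2.6:** use that sum in both compliance formulas. Time between Parts is then outside the denominator and should not be counted as an interruption.
- **SAP 10.4.2.1:** name the summed exposure as the denominator of the exposure-adjusted rates.
- **SAP 9.3:** define the OLE TE Period as the union of the Part A and Part B TE periods.

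The cost is SAP wording and a small programming change. It needs no new data, since the Part-specific definitions already call for first and last dose dates in each Part. If no subject had a gap, exposure and compliance results stay the same.
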